8.5 Study Medication Accountability

An accurate and current accounting of the dispensing and return of study drug for each subject will be maintained on an ongoing basis by a member of the IDS pharmacy service.

9 STUDY PROCEDURES AND GUIDELINES

Prior to conducting any study-related activities, written informed consent and the Health Insurance Portability and Accountability Act (HIPAA) authorization must be signed and dated by the subject.

9.1 Clinical Assessments

9.1.1 Concomitant Medications

All concomitant medication and concurrent therapies will be documented at Baseline/Screening and at each session. Dose, route, unit frequency of administration, and indication for administration and dates of medication will be captured.

9.1.2 Demographics

Demographic information (date of birth, gender, race) will be recorded at Screening.

9.1.3 Medical History

Relevant medical history, including history of current disease, other pertinent respiratory history, and information regarding underlying diseases will be recorded at Screening.

9.1.4 Physical Examination

A complete physical examination will be performed by either the investigator or a subinvestigator who is a physician at Screening.

9.1.5 Vital Signs

Blood pressure, pulse and respirations will be performed after resting for 5 minutes at Screening and at beginning of each session. During sessions, blood pressure, pulse and respirations will be measured every 15 minutes up until two hours after IM injection of study medication.

Version #: 1.9 Version Date: 12/09/2020 Page 16 of 37

9.1.6 Oximetry

Oximetry will be measured on room air with the subject at rest at Screening, at the baseline of each session and every 15 minutes during sessions up until two hours after IM injection of study medication.

9.1.7 Adverse Events

Information regarding occurrence of adverse events will be captured throughout the study. Duration (start and stop dates and times), severity/grade, outcome, treatment and relation to study drug will be recorded on the case report form (CRF).

9.2 Clinical Laboratory Measurements

9.2.1 Pregnancy Test

A urine pregnancy test will be obtained from female subjects who are of childbearing age prior to their participation in the study (Screening) and before each study session.

9.2.2 Urine drug screen

Urine will be collected for urine drug screen at screening and on each session day. Methadone must be positive. Although current illicit drug use is not exclusionary, participants will be informed they will need to have negative urine drug screen at beginning of each session.

9.2.3 Breathalyzer

Participants will provide a breath alcohol test at screening and on each session day. Results must be 0.00 to complete screening and to begin sessions.

9.3 Pupilometer

Pupil diameter is one of the most sensitive measures of opioid withdrawal activity. Pupil diameter will be collected with a pupilometer in ambient room light (NeurOptics, Irvine, California) at baseline and every 15 minutes during sessions up until two hours after IM injection of study medication.

9.4 Impulsivity Measures

9.4.1 Delay Discounting

Delay discounting is the relative preference for smaller sooner over larger later rewards, an aspect of impulsivity. Most individuals would prefer an immediate \$100 over \$100 delayed by 1 year. However, when faced with the choice between receiving \$95 now versus \$100 in 1 year, preferences for the delayed reward may increase. By assessing such choices across multiple delays, delay discounting quantifies the devaluation of rewards over time, which allows for an index of overall discounting rate (k). Delay discounting will be measured 30 minutes after IM injection during each session.

Version #: 1.9 Version Date: 12/09/2020 Page 17 of 37

9.4.2 Validated trait impulsivity measures.

Participants will also be assessed for trait impulsivity using four personality questionnaires assessing impulsivity or closely related constructs during screening. Scales will include the Barratt Impulsivity Scale-11 (85, 86); the Eysenck Impulsivity Questionnaire (87); the Sensation Seeking Scale (88); and the Zimbardo Time Perspective Inventory (89).

9.5 Opioid Withdrawal Measures

These measures are very familiar to the PI ([name]) and utilize standard tools that will be collected by trained research staff. In each session, the opioid withdrawal measures will be collected at baseline and every 15 minutes following IM injection. They include the COWS (23, 107); Subjective Opiate Withdrawal Scale (SOWS) (24), and VAS ratings of subjective drug effects (108, 109).

The COWS is an 11-item rating system that is completed by a trained observer. Total scores range from 0 to 47, and withdrawal is classified as mild (5–12), moderate (13–24), moderately severe (25–36), or severe (>36).

The SOWS is a self-report instrument that asks participants to rate their level of current opioid withdrawal on 16 symptoms using a 5-point Likert scale (Not At All to Extremely). Answers to the 16 items are summed for a total score.

There are six VASs of subjective drug effects: high, drug effect, good effects, bad effects, liking, and sick. Each scale is a 100-point line anchored at one end with "not at all," and at the other with "extremely." The participant positions an arrow along the line using the keypad to indicate his or her answer of how s/he is feeling at that moment.

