| CONCOMMITANT | Beyond their methadone maintenance dose, participants will be |
| MEDICATIONS | allowed to take OTC or prescription strength non-opioid analgesic |
| | medications such as acetaminophen or ibuprofen for pain throughout |
| | the study, consistent with standards of care. |
| | Prohibited : Opioid analgesics other than methadone |
| | - I |

Version #: 1.9 Version Date: 12/09/2020 Page 6 of 37

| EVALUATIONS | | |
|-----------------------|--|--|
| PRIMARY ENDPOINT | Delay discounting of money rate (k) | |
| SECONDARY | Pain VAS ratings (0-100) | |
| ENDPOINTS | Peak COWS | |
| | Peak SOWS | |
| | Peak Change from Baseline Pupil Diameter | |
| | Peak VAS of Subjective drug effects (0-100) | |
| | Drug Effects | |
| | Good Effects | |
| | Bad Effects | |
| | Liking | |
| | • Sick | |
| OTHER | Pain Catastrophizing Scale | |
| EVALUATIONS | Barratt Impulsivity Scale-11 | |
| | Eysenck Impulsivity Questionnaire | |
| | Sensation Seeking Scale | |
| | Zimbardo Time Perspective Inventory | |
| SAFETY | Incidence of adverse events | |
| EVALUATIONS | Change in vital signs from baseline (HR, BP, RR, % oxygen) | |
| | saturation) | |
| PLANNED INTERIM | When approximately 10 patients have completed the study, an interim | |
| ANALYSES | analysis will be conducted by the study statistician. If there is no trend | |
| | of differences in delay discounting between placebo and naloxone | |
| | administration sessions, we would discuss with our NIDA program | |
| | official and independent medical monitor on the following two | |
| | options: increasing the dose of naloxone to 0.15 mg or administering | |
| | 0.1 mg naloxone at trough instead of peak methadone levels. Serious adverse events will be monitored by the medical monitor throughout | |
| | the duration of the study. | |
| STATISTICS | Using methods developed by co-I [name], nonlinear regression will | |
| Primary Analysis Plan | be used to calculate individual values of k, larger k values indicate | |
| Timary Analysis I lan | greater discounting or more impulsiveness. K values are normalized | |
| | using log transformation for parametric analysis. We will use repeated | |
| | measures analyses implemented in SAS PROC MIXED. The | |
| | dependent variable is k (discounting). Independent variables include | |
| | Group (PAIN vs. NO PAIN), a fixed, between-subjects effect and | |
| | Condition (control vs. withdrawal), a repeated, within-subjects effect. | |

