9.6.3 Brief Pain Inventory – Short Form

The BPI (94) is a 9 item self-report questionnaire used to evaluate the severity of a patient's pain and the impact of this pain on the patient's daily functioning. The patient is asked to rate their worst, least, average, and current pain intensity, list current treatments and their perceived effectiveness, and rate the degree that pain interferes with general activity, mood, walking ability, normal work, relations with other persons, sleep, and enjoyment of life on a 10 point scale. The BPI will be used at screening to screen for the presence or absence of chronic pain. Additionally, BPI "pain right now" VAS will be asked at beginning of each session. This score must be 0 for patients with NO PAIN or the session will be rescheduled. PAIN group persons must report similar levels of pain each session (i.e., the BPI "pain right now" score at session 2 must be +/-20% of the "pain right now" score at session 1; PAIN group persons cannot have a "pain right now" score of 0) or the session will be rescheduled.

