10.2 Visits 2-3 (Sessions 1-2)

- 1. Record any Adverse Experiences
- Concomitant medications review
- 3. Collect Urine for UDS (and pregnancy test if female)
- Perform and record "pain right now" VAS from BPI
- 5. Record time of methadone dosing (confirm by reviewing Methasoft EHR)
- 6. Perform and record baseline values of
 - a. Vital signs
 - b. Oximetry
 - c. Pupilometer
 - d. COWS
 - e. SOWS
 - f. Pain VAS
- 7. If smoker, allow participant to smoke 20 minutes prior to study drug administration
- 8. Administer IM study drug. Record on progress note.
- 9. For every 15 minutes until two hours after IM injection, measure
 - a. Vital signs
 - b. Oximetry
 - c. Pupilometer
 - d. COWS
 - e. SOWS
 - f. Pain VAS
 - g. Subjective drug effect VASs

Version #: 1.9 Version Date: 12/09/2020 Page 20 of 37

- 10. 30 minutes after study drug administration, perform and record delay discounting task
- Perform and record PCS
- 12. Perform and record PHQ-15
- 13. Perform and record GAD-7
- 14. Perform and record PHQ-9
- 15. Perform and record Barratt Impulsivity Scale-11
- 16. Perform and record Eysenck Impulsivity Questionnaire
- 17. Perform and record Sensation Seeking Scale
- 18. Perform and record Zimbardo Time Perspective Inventory
- 19. Perform and record Insomnia Severity Index

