14.2 Demographic and Baseline Characteristics

The PAIN and NO PAIN groups will be compared on all matching variables (methadone dose, cigarettes smoked per day, annual income, years of education, and age) using t-tests and chi-square tests as appropriate. If statistically significant differences are detected despite efforts to match during recruitment, matching variables will be included as covariates in subsequent analyses. It is recognized that this method is inferior to formal matching; therefore, substantial effort will be devoted to locating appropriately matched individuals. Measures obtained at 15-minute intervals during each session (pain, vital signs, opioid withdrawal, etc.) will be examined in terms of group comparability and to

Version #: 1.9 Version Date: 12/09/2020 Page 24 of 37

confirm that naloxone precipitated withdrawal symptoms compared to placebo. All psychometric, scaled measures will be scored according to standardized algorithms and internal consistency reliability examined. Given the design of the study, unit level missing data is not anticipated. Item level missing data will be minimized through supervised administration of measures. Missing data patterns will be examined and multiple imputation (SAS PROC MI) or other strategies employed as appropriate. Using methods developed by co-I [name], nonlinear regression will be used to calculate individual values of k, larger k values indicate greater discounting or more impulsiveness. K values are normalized using log transformation for parametric analysis (45).

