14.3 Analysis of Primary Endpoint

The primary hypotheses are that participants with chronic pain (PAIN) are more impulsive (larger k values) than participants without pain (NO PAIN) and that, within the same individual, k values will be larger in the naloxone-precipitated opioid withdrawal session compared to placebo. We will test these hypotheses using repeated measures analyses implemented in SAS PROC MIXED. The dependent variable is k (discounting). Independent variables include Group (PAIN vs. NO PAIN), a fixed, between-subjects effect and Condition (control vs. withdrawal), a repeated, within-subjects effect. The Group x Condition interaction will be examined to determine if group differences vary by condition. Planned contrasts will explore additive effects of chronic pain and withdrawal by examining whether discounting by the PAIN group in the withdrawal condition is greater than 1) discounting by the PAIN group in the control condition, or 2) discounting by the NO PAIN group in the withdrawal condition. To examine the effect of differing levels of peak aversive stimuli on discounting, we will conduct analyses using only data from the naloxone-precipitated withdrawal session that include peak COWS scores.

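### Peak COWS and SOWS carry no baseline term although a pre-injection score is taken in every session; precision is lost in some comparisons, and the naloxone-only analysis cannot isolate precipitated withdrawal

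*Combined protocol and SAP*

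**What the plan says.** The synopsis lists peak COWS and peak SOWS as secondary endpoints with no reference to baseline. In the same list pupil diameter is "Peak Change from Baseline Pupil Diameter". No reason is given for the difference.

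The pre-injection scores exist. Section 9.5 states that "the opioid withdrawal measures will be collected at baseline and every 15 minutes following IM injection". Section 10.2, under "Perform and record baseline values of", names COWS and SOWS among the items for both sessions. That baseline list leaves out one set of measures that 9.5 includes: "Subjective drug effect VASs" appear only in the post-injection list.

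The withdrawal scores have four planned uses:

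- Section 14.2 examines the 15-minute measures for comparability of the PAIN and NO PAIN groups.
- Section 14.2 also uses them to "confirm that naloxone precipitated withdrawal symptoms compared to placebo".
- Section 14.3 relates discounting to symptom level, using only data from the "naloxone-precipitated withdrawal session that include peak COWS scores".
- Section 14.4 looks at sex and opioid withdrawal.

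None of these names a baseline score. The only covariates mentioned are those in 14.2, where "matching variables will be included as covariates in subsequent analyses" if the groups differ significantly on them. Section 14 says that a detailed SAP will be written before the final analysis.

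**The concern.** A peak score is the starting score plus whatever happened after the injection. When each person is compared with himself or herself across two sessions in random order, stable starting symptoms largely cancel. They do not cancel when people are compared with one another.

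Three of the four uses compare people: group comparability, sex, and the naloxone-only analysis. The last matters most for interpretation. It has no placebo session to subtract, and 14.3 names neither baseline COWS nor Group for it. Section 2.1 counts body aches and low mood among withdrawal symptoms. Section 9.6.3 separates the groups by current pain at session start: for the pain-free group, "This score must be 0 for patients with NO PAIN or the session will be rescheduled", and a PAIN participant may not score 0. Section 3 expects PAIN participants to discount more in both sessions. Pain could therefore raise both the starting COWS and k, and so produce an association between peak COWS and k without any effect of naloxone.

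The second stake is precision: a covariate that is already scheduled goes unused.

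**Working it through.** **The plan's own figure.** No power or precision is stated for COWS or SOWS. The stated power (over 80%, alpha 0.05 two-sided) concerns discounting with 100 completers. Inputs from the synopsis and 14.6: f² = 0.02 within, f² = 0.08 between, correlation 0.5, two sessions. Noncentral F with 1 and 98 df:

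- Condition and interaction: λ = 0.02 × 100 × 2 / (1 − 0.5) = 8.0, power 79.97%, on the 80% line.
- Group: λ = 0.08 × 100 × 2 / (1 + 0.5) = 10.67, power 89.9%.

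The stated power is reproduced to within rounding. It does not depend on how COWS and SOWS are handled.

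**Assumptions for the rest.** The documents give no standard deviation or baseline-peak correlation for COWS or SOWS, so every correlation below is assumed. Equal variances are also assumed.

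**(a) COWS or SOWS as outcome, one session or between people.** With baseline as covariate, residual variance is 1 − r² of the raw value. The detectable PAIN versus NO PAIN difference (50 per group, 80% power) is (1.96 + 0.84) × √(2/50) × √(1 − r²), in SD units of the raw peak; without adjustment it is 0.56.

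| r | 1 − r² | Variance cut | 100 completers act like | Detectable difference |
|---|---|---|---|---|
| 0.3 | 0.91 | 9% | 110 | 0.535 SD |
| 0.5 | 0.75 | 25% | 133 | 0.485 SD |
| 0.7 | 0.51 | 49% | 196 | 0.40 SD |

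If one group started 0.2 to 0.4 SD higher (assumed), the part of the raw peak gap carried over from baseline would be gap × r: from 0.2 × 0.3 = 0.06 SD to 0.4 × 0.7 = 0.28 SD.

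**(b) Naloxone-placebo contrast.** Let d be the baseline-peak correlation within a session minus that across sessions, rp the peak-peak correlation and rb the baseline-baseline correlation. Adjusting for the difference in baselines leaves 1 − d² / [(1 − rp)(1 − rb)] of the raw variance. With rp = 0.5:

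- d = 0: 1.00, no gain.
- d = 0.1: 0.96 (rb = 0.5) or 0.93 (rb = 0.7).
- d = 0.2: 0.84 (rb = 0.5) or 0.73 (rb = 0.7).

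The saving is 0 to 27%.

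**(c) Bare change score instead of a covariate.** Between people the variance factor is 2(1 − r): 1.4, 1.0 and 0.6 at r = 0.3, 0.5 and 0.7. In the crossover it is [(1 − rp) + (1 − rb) − 2d] / (1 − rp). At d = 0.1 this is 1.6 for rb = 0.5 and 1.2 for rb = 0.7, both worse than the raw peak.

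**(d) Naloxone-only analysis.** Here k is the outcome and peak COWS a predictor, so the saving in (a) does not apply. Adding baseline COWS multiplies the variance of the peak-COWS coefficient by 1/(1 − r²) = 1.10, 1.33 or 1.96, unless baseline COWS itself explains variation in k.

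**The case against.** The strongest reply has four parts.

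First, the plan gives no explicit model for COWS or SOWS. That they will be analysed raw is read from the endpoint names and from the absence of any baseline term, and the pending SAP could supply one. This stands, and it makes the SAP the natural place for the change.

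Second, 14.3 sets out to study differing levels of peak aversive stimuli, and the primary objective speaks of aversive stressors. Total symptom level is a defensible exposure for that question. This also stands: the planned analysis is not an error. What it cannot do alone is attribute an association to the withdrawal that naloxone produced.

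Third, a reader might infer that the raw naloxone-placebo contrast is biased, or that precision is lost in every withdrawal comparison. The design does not support either. Session order is randomised, stable symptoms cancel within a person, and the gain from adjustment may be nil.

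Fourth, a reader might take the current-pain rule in 9.6.3 as proof that PAIN participants start with higher COWS or SOWS. That rule concerns an item of the Brief Pain Inventory. Nothing in the documents says that baseline withdrawal scores differ by group, so the carry-over in (a) is a possibility only. The same rule makes baseline pain VAS a poor covariate for comparing the groups on pain VAS: the two groups would hardly overlap, and the adjusted difference would be an extrapolation.

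**Conclusion.** The point holds in a limited form. COWS and SOWS are defined as raw peaks, their baselines are scheduled in both sessions, and no analysis section uses them.

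- Naloxone-placebo contrast: unbiased; the loss is of precision only, 0 to 27% of variance under the assumed correlations.
- Between-person comparisons of COWS or SOWS: adjustment would cut residual variance by 9%, 25% or 49% at assumed r of 0.3, 0.5 or 0.7. Which value applies cannot be learned from the documents.
- Naloxone-only analysis: an association of raw peak COWS with k cannot by itself be credited to precipitated withdrawal. It would go too far to call the analysis invalid, or to promise it more precision from adjustment; its coefficient may become less precise.
- Subjective-effect scales: 9.5 requires a baseline and the 10.2 list omits it, so those data are not assured.

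These are secondary and supportive analyses. The primary Group x Condition test and the sample size do not change.

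**What to change.** 1. In 14.2 to 14.4, or in the pending SAP, state that peak COWS and peak SOWS will be modelled with the same-session pre-injection score as covariate. In the crossover model, enter both sessions' baselines or their difference. Do not replace the peak with a bare change score.
2. In the naloxone-only analysis of 14.3, keep peak COWS as planned and add a sensitivity model that also contains baseline COWS. Say in advance that the peak-COWS coefficient may be less precise there.
3. Do not adjust the PAIN versus NO PAIN comparison of pain VAS for baseline pain.
4. Reconcile 9.5 with 10.2 by adding the subjective-effect VAS to the baseline list in 10.2.

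Items 1 to 3 cost SAP wording and one or two degrees of freedom per model; the COWS and SOWS baselines are already scheduled. Item 4 costs one extra set of short ratings per session. It cannot be made good later for sessions run without it. Fixing the choice before the final analysis also prevents a choice between raw and adjusted peaks once results are known.

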9.6 Pain Measures

9.6.1 Pain VAS

Ratings are completed on a computer; using a mouse. The participant positions an arrow along a 100 mm line marked at either end with "none" and "worst pain imaginable." Ratings will be collected at Screening, session baseline and every 15 minutes during sessions up until two hours after IM injection of study medication.

9.6.2 Pain Catastrophizing Scale

The Pain Catastrophizing Scale (PCS) is a 13-item scale that assesses important affective and cognitive aspects of pain.43 The PCS instructions asked participants to reflect on past painful experiences and to indicate the degree to which they experienced a particular thought or feeling when experiencing pain. Responses were rated on a 5-point scale from 0 ("Not at All") to 4 ("All the Time"). Pain Catastrophizing Scale scores range from 0 to 52, with higher scores indicating heightened distress responses when exposed to aversive stimuli. The PCS will be measured in Session 1.

Version #: 1.9 Version Date: 12/09/2020 Page 18 of 37

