5.2 Secondary Efficacy Endpoints

Secondary outcome variables will include measures of pain and opioid withdrawal, i.e.

- Pain Visual Analog Scale (VAS)
- Clinical Opiate Withdrawal Scale (COWS)
- Subjective Opiate Withdrawal Scale (SOWS)
- Vital Signs
- Pupil Diameter
- VAS Ratings of Subjective Drug Effects

In addition, personality questionnaires assessing impulsivity will be collected at screening and compared across groups, including

- Barratt Impulsivity Scale-11
- · Eysenck Impulsivity Questionnaire
- Sensation Seeking Scale
- Zimbardo Time Perspective Inventory

In addition, pain catastrophizing will be assessed and will be a main predictor variable in the linear regression models assessing effect modification in study Aim 2.

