10 EVALUATIONS BY VISIT

10.1 Visit 1 (Screening)

- 1. Review the study with the subject and obtain written informed consent and HIPAA authorization
- Assign the subject a unique screening number
- 3. Collect urine for urine drug screen (and pregnancy test if female)
- 4. Collect ROI for opioid treatment program
- Record demographics data
- 6. Record medical history
- Record drug use history
- Record concomitant medications

Version #: 1.9 Version Date: 12/09/2020 Page 19 of 37

- 9. Perform a complete physical examination
- 10. Perform and record vital signs
- 11. Perform and record oximetry
- Perform and record EKG
- 13. Perform and record MINI
- 14. Perform and record BPI
- 15. Perform and record NHANES Miscellaneous Pain Questionnaire
- 16. Perform and record Widespread Pain Index
- 17. Perform and record BPI
- 18. Schedule subject for Visit 2 (Session 1) as appropriate.
- 19. Randomize subject

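### The timing of the pain catastrophizing score is inconsistent, and no section places it before the first injection, although 14.4 uses it as the trait moderator of the withdrawal effect

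*Combined protocol and SAP*

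**What the plan says.** **PCS.** Section 9.6.2 states "The PCS will be measured in Session 1" and gives no position relative to the injection. Section 10.2, headed "10.2 Visits 2-3 (Sessions 1-2", is one list for both sessions. It has "Perform and record PCS" as item 11, after the injection (item 8) and after item 10, "30 minutes after study drug administration, perform and record delay discounting task". Item 6, "Perform and record baseline values of", covers vital signs, oximetry, pupil, COWS, SOWS and pain VAS, but not PCS. The screening list in 10.1 has pain instruments such as "Perform and record Widespread Pain Index", but not PCS.

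**Role of PCS.** The synopsis and 3.2 call it a trait moderator. Section 14.4 reads a significant Condition-by-PCS interaction as effect modification. The synopsis limits this objective to the PAIN group; 3.2 does not, and the hypothesis in section 3 spans both groups.

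**Other scales.** Section 9.7 puts PHQ-15, PHQ-9 and GAD-7 at Session 1, whereas 10.2 lists them without restriction. For trait impulsivity, 5.2 says that "personality questionnaires assessing impulsivity will be collected at screening and compared across groups", and 9.4.2 agrees. Yet 10.1 omits all four scales and 10.2 lists them at the sessions.

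**COWS.** Item 9 of 10.2 reads "For every 15 minutes until two hours after IM injection, measure", and COWS is among the measures. An additional analysis in 14.3 uses peak COWS from the naloxone session, with no time window.

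**The concern.** A moderator should be fixed before the treatment whose effect it is said to modify. Section 4.1 randomises session order, so Session 1 is the naloxone session for some participants. If PCS is rated once, after the Session 1 injection, those participants rate it after precipitated withdrawal and the others after saline. If people with stronger withdrawal both rate themselves higher and show a larger change in discounting, PCS and the change become correlated with no true moderation behind it. If PCS is rated at both sessions, 14.4 does not say which score enters the model.

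The Aim 2 conclusion is at stake, together with the description of PCS as a trait. There is also an operational problem: staff who follow section 10 would not collect the impulsivity scales at the visit that 5.2 and 9.4.2 name.

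**Working it through.** **1. The plan's own figure.** The synopsis claims more than 80% power with 100 completers, two-sided alpha 0.05 and repeated-measures correlation 0.5. For condition and interaction, λ = 0.02 × 100 × 2 / (1 − 0.5) = 8, and F(1, 98) gives 0.80. For group, λ = 0.08 × 100 × 2 / (1 + 0.5) = 10.67, which gives 0.90. The figure reproduces and is not in question. The plan gives no figure for the PCS test.

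**2. Timing, side by side.**

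| Measure | Descriptive section | 10.1 screening | 10.2 sessions |
|---|---|---|---|
| PCS | Session 1 (9.6.2) | absent | both sessions, listed after injection and task |
| PHQ-15, PHQ-9, GAD-7 | Session 1 (9.7) | absent | both sessions, listed after injection and task |
| Four impulsivity scales | screening (5.2, 9.4.2) | absent | both sessions, listed after injection and task |

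The 10.2 list is not strictly chronological: item 9 runs to 120 minutes and item 10 is due at 30. PCS after the injection is therefore the likely reading, not a stated one.

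**3. Possible size of the bias.** The documents give no PCS shift after naloxone, so all inputs here are assumptions except the correlation of 0.5. Set the SD of log k to 1; the SD of the within-person change is √(1 + 1 − 2 × 0.5) = 1. Assume half the participants receive naloxone first. In them, observed PCS = trait + s + e × severity, and severity correlates b with the change in log k. There is no true moderation. Then

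r = ½eb / √(1 + ¼s² + ½e²), δ = r√N, false-positive rate ≈ Φ(−1.96 + δ) + Φ(−1.96 − δ).

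- s = 0.5, e = 0: r = 0, so the rate stays at 5%.
- s = 0.2, e = 0.1, b = 0.3: r = 0.015/√1.015 = 0.0149; at N = 100, δ = 0.15 and the rate is 5.3%.
- s = 0.5, e = 0.3, b = 0.3: r = 0.045/√1.1075 = 0.0428; δ = 0.43; 7.1%.
- s = 0.5, e = 0.5, b = 0.4: r = 0.100/√1.1875 = 0.0918; δ = 0.92; 15.1%.

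Simulation of the regression of change on PCS (20,000 runs per case) agrees:

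| Case | N = 100 | N = 50 (PAIN only) | N = 100 with session-order term |
|---|---|---|---|
| No contamination | 5.1% | 5.1% | 5.0% |
| s 0.5, e 0 | 5.3% | 4.9% | 5.4% |
| s 0.2, e 0.1, b 0.3 | 5.3% | 5.1% | 5.3% |
| same, plus session effect of −0.1 SD on log k | 5.6% | 5.4% | 5.2% |
| s 0.5, e 0.3, b 0.3 | 7.0% | 6.1% | 7.1% |
| s 0.5, e 0.5, b 0.4 | 15.3% | 9.8% | 15.8% |

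The session-order term removes the uniform shift s, not the severity-linked part e, so it does not help where help is needed.

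**4. Power.** As a placeholder, take a true moderation of √0.08 = 0.283 SD per SD of PCS. Power is 79% at N = 100 and 50% at N = 50. A uniform 0.5 SD shift lowers the 79% to 76%. Saline-first participants alone give 48% (n = 50) and 27% (n = 25).

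**5. COWS.** 120 / 15 = 8 post-injection readings. Those at 45 to 120 minutes, 6 of the 8, follow the 30-minute task. This counts readings; it does not say how often the peak is late.

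**The case against.** **Drafting.** Section 10.2 pools two visits, and a specific sentence such as that in 9.6.2 would ordinarily govern a pooled checklist. The lists are loose in other ways too: 10.1 has the BPI twice. This weakens the claim that PCS is taken twice. It does not supply a pre-injection time, because 9.6.2 gives none.

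**No harm shown.** The PCS asks about past pain, section 1.1 calls catastrophizing relatively stable, and 8.4.1 describes naloxone as inducing mild withdrawal. A reader might infer that the moderation test is invalid or that its error rate is 15%. The documents support neither: moderate inputs give about 5%, and the 7 to 15% cases rest on assumed severity-linked contamination of 0.3 to 0.5 SD. If the 14.4 GLM is fitted without a subject term, every case simulated falls below 5% (0.6 to 3.4% at N = 100). This objection stands as to size. It does not remove the reason for a change that costs little.

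**Peak COWS.** A reader might also infer that peak COWS is the wrong predictor and should be replaced. Section 14.3 deliberately targets peak aversive stimuli, and the documents give no withdrawal time course. Under an assumed single-peaked curve, the better proxy for severity at 30 minutes depends on the inputs. With reading-error SD 2, a mean peak at 60 minutes and peak-time log-SD 0.15, peak COWS correlates 0.81 with it and the 30-minute reading 0.74. With log-SD 0.25 the order reverses (0.70 against 0.77). Replacement is not justified, and neither is adding placebo-session log k as a covariate: it would set aside the plan's restriction to naloxone-session data without an assured gain in precision.

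**Conclusion.** The inconsistency is in the text, and no section places PCS before the first injection. Under random order, a single Session 1 score would probably follow naloxone in some participants; about half is a figure that needs the unstated 1:1 ratio. The resulting bias in the Condition-by-PCS test is unknown and may be near zero. The simulated range is about 5% false positives for uniform or small shifts, and 7 to 15% at N = 100 (6 to 10% at N = 50) under strong severity-linked contamination. The documents do not establish that PCS is in fact rated after naloxone, or that the error rate is inflated.

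The point concerns a secondary analysis and the schedule; the primary Group x Condition test is unaffected. It is worth correcting because the sections must be reconciled anyway, and collection at Visit 1 removes the question. The COWS timing is an optional refinement.

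**What to change.** 1. Collect PCS and the four impulsivity scales at Visit 1, before any injection. State one pre-injection time for PHQ-15, PHQ-9 and GAD-7. Make 5.2, 9.4.2, 9.6.2, 9.7, 10.1 and 10.2 agree.
2. For PCS already collected, record the session and the time relative to injection. Report a saline-first analysis as a low-power sensitivity check only. Do not rely on a session-order term as a correction. Do not rely on a Session 2 saline score either: in naloxone-first participants it still follows naloxone exposure.
3. Optional, in the SAP that section 14 promises: keep peak COWS as planned in 14.3 and add the 30-minute COWS as a sensitivity analysis.

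Cost: no new measures. Screening would run longer than the stated 3 hours. Some of the roughly 200 − 130 = 70 people screened but not enrolled (6.1) would complete questionnaires that are never analysed. Items 1 and 2 need one minor amendment with IRB approval (16.1). If the PHQ and GAD scales stay in Session 1, placing them before the injection makes the pre-task procedures differ between sessions, which 4.1 intends to be the same; placing them at Visit 1 avoids this but measures symptoms earlier.
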